#### **Group and individual phone arms.**

**Diet-Weight loss (0-6 mos.).** Energy intake will be prescribed at 1,200-1,500 kcal/d for women and 1,500-1,800 kcal/d for men as recommended by current weight management guidelines from the American Heart Association/American College of Cardiology/The Obesity Society (30). Participants will be asked to consume a minimum daily total of two portion controlled entrées (~200 to 300 kcal each, saturated fat ≤ 3g, sodium ≤ 600 mg), two low calorie shakes (~100 kcal

each), at least five one-cup servings of fruits/vegetables, and ad libitum non-caloric beverages to achieve their energy reduction goals. Participants will be asked to purchase entrées from a list maintained by the study dietician that satisfies these caloric/fat/sodium requirements, as well as fruits/vegetables, and non-caloric beverages. Two low calorie shakes per day (Profile by Sanford Health, Sioux Falls, SD) will be provided to participants during weight loss (0-6 mos.). Participants will order shakes, which are available in a variety of flavors, either on-line or by telephone. Shakes will be delivered by the United Parcel Service to participant's residence. The study will provide the shakes and shipping during weight loss (0-6 mos.) The list of available frozen and shelf stable entrées currently contains over 180 entrées from numerous manufacturers, e.g., Healthy Choice™, Smart Ones™, Michelina's™ etc., which meet the caloric, saturated fat and sodium requirements. This list will be updated by the study dietician as new products become available. The recommended entrées are affordable and available at most grocery stores at a cost of \$2-\$4 each, which may be an important consideration for individuals in rural areas where household income is often low (6). The Academy of Nutrition and Dietetics Evidence Analysis Library indicates strong, consistent, supportive evidence (Grade I) that a portion controlled entrée approach results in significantly greater weight loss and maintenance compared with meal plan diets, and are especially useful for individuals who have difficulty with food selection and portion control (59). This approach simplifies food shopping and preparation, and can be incorporated as part of a long-term dietary plan. The nutritional information on the product labels (calories, fat, protein, etc.) simplifies adherence to specific energy and nutrient recommendations. The use of portion controlled entrées and shakes for weight loss has been criticized for inadequately preparing participants to deal with meal planning and portion control required for successful weight loss maintenance. However, this approach requires decision making regarding shopping and preparation of fruit/vegetables, beverages and also provides participants with an understanding of appropriate portion size. Numerous trials by our group (34, 48, 60) and others (61-63) have reported excellent maintenance of weight initially lost using portion controlled entrées and low calorie shakes. The study dietician will assure that all diets are both energy and nutritionally adequate based on current dietary guidelines (64). Participants for whom additional weight loss would be contraindicated, e.g., BMI of  $\leq 22 \text{ kg/m}^2$  will be placed on a weight maintenance diet at any time during the 18 mo. intervention. Those who continue to lose weight will be referred to appropriate health professionals/agencies, and may be dismissed from the trial.

**Diet- Weight maintenance and no-contact follow-up (7-24 mos.).** Participants will be encouraged to consume a diet with an energy level designed to maintain weight loss. Recommended EI will be based on the resting metabolic rate (RMR) equation of Mifflin-St Jeor (65) adjusted for activities of daily living (RMR x 1.4-1.6) as participants will have a routine PA program. Participants will be encouraged to continue using commercially available portion controlled entrées, low calorie shakes, or transition to a meal plan or combination portion controlled entrée/meal plan diet. A meal plan diet, based on the United States Department of Agriculture's MyPlate guidelines (66) will prescribe amounts of grains, proteins, fruits, vegetables, dairy, and fats to achieve the desired level of EI. Participants experiencing weight gain will be counseled to improve compliance with the diet and PA protocols.

**Physical activity (0- 24 mos.).** We will prescribe a progressive moderate intensity PA program, e.g., brisk walking, jogging, biking, etc., as recommended in the "2009 ACSM Position Stand on Physical Activity Interventions for Weight Loss and Prevention of Weight Regain in Adults" (67). The prescribed activities can be completed in rural communities that frequently lack public or commercial exercise facilities. Prescribed PA will progress from 45 min/wk. during week 1 to 225 min/wk. at 4 mos. and remain at 225 min/wk. for the duration of the 18 mo. intervention and 6 mo. no contact follow-up. As the intervention progresses, participants will be

encouraged to try new activities and/or target an event such as a 5 or 10K race, charity walks, etc., to provide variety and motivation. Pedometers will be provided as a motivational tool and to track steps across the 18 mo. active intervention.

**Self-monitoring.** Participants will be asked to self-monitor diet, i.e., the number of portion controlled entrées, shakes and servings of fruits and vegetables/day, PA, i.e., pedometer steps, self-report minutes of activity, and body weight across the 6 mo. weight loss and 12 mo. weight maintenance interventions. Participants will report this data twice each week using a web-based form on our laboratory website or by phone calls to health educators for those without internet access. This information will be summarized by research staff and made available to clinic health educators for use during behavioral counseling sessions.

**Group phone intervention: Delivery/session content.** The GP intervention will be delivered to 12-15 participants during a 45 minute call weekly from 0-6 mos. and biweekly from 7-18 mos. using the MaestroConference® software platform (Oakland, CA) that allows group audio conferences to be accessed by phone. Approximately five minutes prior to scheduled meetings, typically late afternoon or early evening, participants will call a toll-free line and enter a unique code number to join the meeting. Participants will be required to remain on the call for the duration of each session to be considered as having attended the session. Call duration for each participant is monitored by the Maestro software. Each meeting will include a check-in question to generate discussion regarding diet and PA, a review of participants self-monitored diet, weight and PA data reported since the previous meeting, a lesson on a weight management topic, and an experiential learning assignment requiring problem solving, or the practice of behavioral strategies, to be completed prior to the next meeting. Sample topics include: energy density (increase volume, not calories), obtaining fruits and vegetables in rural communities, exercising in rural communities, eating/exercising on the go, etc. Several sessions at the end of the weight loss phase (mo. 6) will include discussions regarding complying with a conventional diet, i.e., meal planning, food shopping, meal preparation, portion control, etc. During weight maintenance (7-18 mos.) group sessions will focus on planning and following a meal plan diet with or without incorporation of portion controlled entrées/shakes, and cardinal behaviors for successful weight maintenance such as self-monitoring, regular PA, eating on weekends/vacations, and controlling EI on special occasions and holidays, etc.

**Individual phone intervention: Delivery/session content.** The IP intervention will be delivered via brief, i.e., ~15 min. scheduled phone calls weekly from 0-6 mos. and biweekly from 7-18 mos.. Prior to each call participants will be asked to read a lesson in the study notebook. Lesson topics will parallel those in the GP intervention and focus on weight loss over mos. 0-6 and weight maintenance during mos. 7-18. During each call, health educators will highlight the major points of the lesson, review self-monitoring data relative to weight, diet and PA, and problem solve, if necessary. Thus, the IP intervention is predominately self-directed with minimal education and support from the health educator. In contrast, the GP intervention includes health educator directed, 45 min educational/behavioral sessions, and provides both health educator and group support.

### **Enhanced usual care**

**Delivery/session content.** Health educators will conduct individual face-to-face meetings (~45 min) at the clinic site, four times across 18 mos. These sessions will be held in conjunction with outcome assessments to minimize participant travel. Participants will receive printed materials from public health organizations such as the Weight-Control Information Network (68) and NIH Aim for a Healthy Weight (69) that include topics such as healthy eating, portion size, and MyPlate recommendations, (i.e. being physically active, self-monitoring, and problem-solving) (66). Pedometers and forms to self-monitor weight, diet and PA will also be provided; however,

self-monitoring will not be required and will be shared with health educators only if desired. During each session health educators will discuss participant's progress towards their weight loss goals, review salient points from the written materials, assist participants with developing strategies to overcome any compliance barriers they may experience, and answer questions.

**Diet-Weight loss (0-6 mos.).** Energy intake will be prescribed at 1,200-1,500 kcal/d for women and 1,500-1,800 kcal/d for men using a high volume, lower fat diet (20-30% EI) meal plan diet as recommended by the Academy of Nutrition and Dietetics (70) and the USDA's MyPlate approach (66). Participants will be provided examples of meal plans consisting of suggested servings of proteins, grains, fruits and vegetables, dairy, and fats based on their energy needs, and will be counseled on appropriate portion sizes.

**Diet- Weight maintenance and no-contact follow-up (7-24 mos.).** Participants will be encouraged to continue with a meal plan diet with an energy level designed to maintain weight loss. Recommended EI will be based on the RMR equation of Mifflin-St Jeor (65) adjusted for activities of daily living (RMR x 1.4-1.6) as participants will have a routine PA program. Meal plans with suggested servings of protein, grains, fruits and vegetables, dairy, and fats to achieve specific energy requirements will be provided. Similar to the GP and IP arms, a participant for whom additional weight loss would be contraindicated, e.g., BMI of  $\leq 22 \text{ kg/m}^2$  will be placed on a weight maintenance diet at any time during the 18 mo. intervention. Those who continue to lose weight will be referred to appropriate health professionals/agencies, and may be dismissed from the trial.

**Physical activity (0- 24 mos.).** Participants will be asked to complete moderate intensity PA, e.g., walking, jogging, biking etc., that will progress gradually from 45 min/wk. at baseline to 150 min/wk. at mo. 4 and remain at 150 min/wk. for the duration of the 24 mo. trial. The 150 min/wk. is based on the current U.S. Department of Health and Human Services PA guidelines of 150 min/wk. of moderate-intensity PA for overall health (71). We recognize that this recommendation differs from the 225min/wk. recommended for the GP and IP arms. Based on our observations of both rural and urban health clinics, physicians and staff rarely recommend greater than 150 min/wk. of PA for their patients. Thus, we chose 150 min/wk. to represent "real world" clinical practice.

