### **Outcome assessments.**

Outcomes will be obtained at each participating clinic. As outlined in Table 3, most outcomes will be assessed at 0, 6, 12, and 18 months. Physical measures, i.e., height, weight, waist circumference, and blood pressure, will be obtained between 7-11 a.m., following a minimum 12-hour fast, by trained research assistants blinded to condition. Research assistants will receive refresher training and complete reliability assessments for physical measures two to three times each year.

**Anthropometric measures.** Weight will be measured with a digital scale accurate to  $\pm 0.1 \text{ kg}$  (Befour Inc. #PS6600, Saukville, WI) with participants in a hospital gown. Height will be measured with a stadiometer (Model #IP0955, Invicta Plastics Limited, Leicester, UK). The average of two measures within 0.25 cm will be recorded. Body mass index (BMI) will be

calculated as weight (kg) divided by height ( $m^2$ ). Waist circumference will be measured with an anthropometric tape using the procedures described by Lohman et. al. (72). Three measurements will be obtained with the outcome recorded as the average of the closest 2 measures.

**Blood chemistry/ blood pressure.** Fasting blood samples will be obtained by a clinic phlebotomist. Analysis of HDL and LDL cholesterol, triglycerides, glucose, and HbA1c (diabetics) will be completed by the commercial laboratories that are contracted by each participating clinic. Blood pressure will be obtained in duplicate, with an automated sphygmomanometer (DinaMap ProCare 100, General Electric Healthcare, Chicago, IL) using the National Health and Nutrition Examination Survey (NHANES) blood pressure protocol (73).

**Compliance with diet recommendations.** Energy and macronutrient intake will be assessed using the self-administered, web-based VioScreen Graphical Food Frequency System (Viocare Technologies, Inc., Princeton, NJ). Participants will complete the survey at a computer in a private room during the clinic assessment visit, or at home on a tablet or personal computer within one or two days following the clinic visit. Participants who fail to complete the survey within that time frame will receive email and telephone reminders. Assessment of nutrient intake using VioScreen is correlated with assessments obtained from a traditional paper and pencil food frequency questionnaire: total fat = 0.82, saturated fat = 0.84, protein = 0.67, carbohydrate = 0.79, alcohol = 0.90 (74).

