**Compliance with physical activity recommendations.** Participants will wear an ActiGraph Model GT3X+ (ActiGraph LLC, Pensacola, FL) portable tri-axial accelerometer on a belt over the non-dominant hip, at the anterior axillary line, during waking hours for seven consecutive days, with the exception of bathing, swimming and contact sports. The ActiGraph accelerometer has been shown to provide valid and reliable assessments of PA in adults (75-77). A 7-day monitoring period provides a reliable estimate of moderate-to-vigorous PA (78-80). ActiGraphs will be initialized and downloaded using ActiLife Software version 6.13.3 or higher and set to collect in the raw data mode at 60 Hz. ActiGraph data will be processed using the protocol used for adults in the 2003-2004 and 2005-2006 cycles of NHANES (81, 82). Data will be aggregated over 60-sec epochs. The following intensity cut-points will be used: sedentary (< 1.0 METs;  $\leq$  100 counts/min), light (1.1-2.99 METs; 101-2019 counts/min.), moderate (3.0-5.99 METs; 2020-5998 counts/min) and vigorous  $\geq$  6 METs;  $\geq$  5999 counts/min) (81, 82). Non-wear time will be defined as at least 60 consecutive minutes of zero counts, with allowance for 1-2 min. of counts between 0 and 100. Counts  $\geq$  20,000/min will be considered spurious and will be deleted (83). We have a custom SAS program to complete these analyses. ActiGraphs, with instructions on their use, will be distributed to participants at their scheduled assessment visit clinic. Participants will be asked to wear the ActiGraph for seven consecutive days, beginning the day following the clinic visit, and return the ActiGraph to the research team using a postage pre-paid padded envelope provided.

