**Questionnaires.** The following instruments will be used to assess behavioral factors that may impact weight management: Health Related Quality of life (HRQOL) will be assessed using the Short Form 36 (SF36) (84). Daily stress associated with eating, i.e., planning/preparing, monitoring nutrients, concerns about eating correctly, will be assessed with the Nutrition Hassles Questionnaire (85). Finally, the implementation of Social Cognitive Theory will be assessed by measuring the “active” ingredient, self-efficacy, using the Weight Efficacy Lifestyle Scale (WELS) (86), Barriers Self Efficacy (BARSE) (87), and the Exercise Self-Efficacy Scale (EXSE) (88). Acceptable construct validity and internal consistency of these instruments have been established (84, 85, 87-90). Questionnaires will be completed online using REDCap

software during the clinic visit by participants with no home internet access or at home within one or two days following the clinic visit for participants with home internet access.

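### Enhanced usual care counselling shares the outcome visit, so in that arm the activity week and home-completed surveys tend to follow a rare counselling session

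*Combined protocol and SAP*

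**What the plan says.** **EUC contact.** Under Enhanced usual care, the arm receives "individual face-to-face meetings (~45 min) at the clinic site, four times across 18 mos". The plan adds: "These sessions will be held in conjunction with outcome assessments to minimize participant travel". In each session the health educator reviews progress and the written materials, and is also to "assist participants with developing strategies to overcome any compliance barriers they may experience, and answer questions".

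**Assessment times.** Under Outcome assessments, "most outcomes will be assessed at 0, 6, 12, and 18 months".

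**Timing of the behavioural measures**, all under Outcome assessments:
- Activity: "Participants will be asked to wear the ActiGraph for seven consecutive days, beginning the day following the clinic visit".
- Diet (VioScreen): in a private room during the visit, or "at home on a tablet or personal computer within one or two days following the clinic visit".
- Questionnaires (SF-36, Nutrition Hassles and three self-efficacy scales): during the visit for those without home internet, and "at home within one or two days following the clinic visit for participants with home internet access".

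**Contact in the other arms.** The GP and IP delivery sections schedule calls weekly in months 0-6 and biweekly in months 7-18. They do not link the calls to assessment visits.

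**Analysis.** The analysis plan compares the questionnaires among the three arms with a mixed linear model. It names no between-arm test for accelerometer or VioScreen data, which are described as compliance measures.

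**The concern.** The timing of measurement relative to counselling differs by arm. In EUC, the activity week and any home-completed survey come straight after the session held at the visit. The plan schedules only four such sessions, so about six months separate them. In GP and IP, contact is frequent enough that the days after a visit resemble any other days. Randomization does not remove a difference that the visit procedure itself creates.

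Suppose a face-to-face session briefly raises activity, confidence or favourable self-report. EUC would then look better on these measures than it did over the preceding months, and the difference from IP or GP would shrink. The self-efficacy scales are the most exposed: the sessions work on overcoming barriers, and one of the scales measures confidence in overcoming barriers to exercise. The plan treats self-efficacy as the active ingredient of its theoretical model, so a blurred contrast there would make a weight difference harder to interpret.

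**Working it through.** **The plan's own figures.** It gives no expected difference or standard deviation for activity, diet or the questionnaires, so there is no stated figure for this point to reproduce. Its power figures concern six-month weight. With SD 7 kg, two-sided alpha 0.025 and differences of 6 kg (80 vs 40) and 4 kg (80 vs 80), the noncentral t gives 98.4% and 91.0%, against 98% and 91% stated. For completers (64 vs 32 and 64 vs 64) it gives 95.2% and 83.1%, against 95% and 83%. These figures reproduce and play no part below.

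**Step 1: when the EUC sessions fall.** There are four sessions across 18 months, held with outcome assessments, and four assessment times up to 18 months (0, 6, 12, 18). The counts match one to one. This is an inference: the text does not list session months, and Tables 2 and 3 are not in the text available for review.

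**Step 2: how unusual the measured EUC week is.**
- Weeks in 18 months: 18 × 365.25 / 12 / 7 = 78.3.
- EUC weeks directly after a session: 4 / 78.3 = 5.1%. The week after an 18-month session begins as that period ends; counting only the other three gives 3 / 78.3 = 3.8%.
- Wear weeks at 6, 12 and 18 months that directly follow a session: all three, on the schedule in step 1.

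**Step 3: the same for GP and IP.**
- Months 0-6: about 26 weekly calls, so every week follows a call.
- Months 7-18: about 52 / 2 = 26 biweekly calls, so about half the weeks follow a call.
- Total: about 52 calls. A measured week is close to a typical week for these arms.

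**Step 4: which measures are exposed.**

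| Measure | Order relative to a session at the same visit |
|---|---|
| Accelerometer week | Always after |
| VioScreen or questionnaires at home | After, by one or two days |
| VioScreen or questionnaires in clinic | Not stated |
| Fasting weight, blood measures | Taken at the visit; same-visit counselling cannot plausibly change them |

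**Step 5: direction.** Let D be the true IP minus EUC difference in change on a scale where higher is better. Let b be the short-lived EUC lift at follow-up, and b0 the lift at baseline.
- Clean baseline: expected measured difference = D − b. With b > 0 and D > 0 this is biased towards no difference, as long as b is not larger than D.
- Baseline also after a session: expected measured difference = D − (b − b0). The bias is smaller if b0 lies between 0 and b, cancels if b0 = b, and reverses if b0 > b.

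Neither b nor b0 can be obtained from the documents, so the calculation stops at direction.

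**The case against.** The strongest points on the other side are these.

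- **Survey order is only partly fixed.** VioScreen may be done during the visit, and participants without home internet complete the questionnaires there. A reader might infer that all EUC surveys follow counselling. The text supports that only for home completion. This stands, although the unstated order is itself a gap.
- **The session months are inferred.** This also stands. The match of four sessions to four visits is strong, but the missing tables could add detail. That GP and IP calls are unlinked to visits is likewise read from the absence of any link.
- **The direction is not certain.** A month-0 session before baseline wear could offset part of the effect in change scores. The plan does not say whether arm is known before baseline wear. This stands and limits the conclusion to probable direction at follow-up.
- **Activity and diet have no planned between-arm test.** Correct. For them the issue is how descriptive compliance data are read. The questionnaires do have a planned comparison.
- **A food frequency instrument is not a record of the days after the visit.** Fair. Any effect on VioScreen would come through reporting rather than through changed intake in those days.
- **Holding sessions with assessments spares rural participants travel.** A good reason, and most of the remedy keeps the single trip.

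A reader might also try to size the effect by assuming that a session adds 20 to 40 minutes of activity in that week, and setting this against the prescribed contrast of 225 − 150 = 75 min/week (20/75 = 27%, 40/75 = 53%). The documents do not support that. They give no source for such a rise, and 75 minutes is a prescribed contrast, not an expected measured one.

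**Conclusion.** The concern holds in limited form. Under the stated timing, EUC activity weeks and home-completed surveys follow a rare counselling session, and nothing comparable happens in GP or IP. This can bias EUC comparisons on the questionnaires and the reading of the activity and diet compliance data, probably towards no difference at follow-up.

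The conclusion assumes that the four sessions coincide with the four visits, that a session has some short-lived favourable effect on behaviour or self-report, and that any baseline lift is smaller than the follow-up lift. The documents describe the visit schedule; they do not show that such an effect occurs. Its size cannot be computed from them.

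A reader might infer that the trial's main result is at risk. It is not: weight and the blood measures are not affected, and neither is GP versus IP on any outcome. The matter still merits a change rather than a note. On the inferred schedule, EUC activity at 6, 12 and 18 months is never measured away from a session, so analysis could not correct it afterwards.

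**What to change.** Amend the visit procedure as follows.

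1. **Surveys, all arms.** Have VioScreen and the REDCap questionnaires completed in the days before the visit, or at the clinic before any session.
2. **EUC session.** Make it the last item of the visit, after all measures.
3. **Accelerometer at follow-up, all arms.** Mail the device so that the seven days of wear end by the visit, and collect it there.
4. **Baseline.** Complete surveys and wear before arm is disclosed and before the first EUC session.

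**Cost.** Items 1 and 2 are cheap and keep the single trip. Item 3 replaces return postage with outbound postage, gives up the in-person hand-over at follow-up, and will leave some incomplete records. Repeat wear after the visit would bring the problem back, so such records should be flagged. Item 4 is harder. Eligibility is not final until baseline testing, so a device issued earlier, for example at the in-person screening meeting after consent, will sometimes go to a person who proves ineligible. A device issued at baseline testing means the first EUC session must wait until wear is complete, which may require another trip.
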